#### **Figure 4: Study Schema**

After 6 months of goserelin and enzalutamide therapy, all men will have a second mpMRI examination. The primary goal being to create the 3D mold prior to prostatectomy and the secondary to obtain the post treatment mpMRI data.

### **1.9 DRUG ADMINISTRATION**

#### **1.9.1 Enzalutamide**

All patients will receive enzalutamide 160mg orally, daily for 24 weeks. Enzalutamide may be administered with or without food. The study drug will be dispensed by the institutional pharmacy.

#### **1.9.2 Goserelin**

Goserelin will be administered SC for a total of 24 weeks. The following are examples of acceptable regimens (no dose modifications will be permitted):

Goserelin 10.8mg administered subcutaneously every 12 weeks (2 doses).

(Equivalent forms of ADT would also be acceptable including other GnRH agonists/antagonists)

### **1.10 DOSE MODIFICATIONS**

#### **1.10.1 Enzalutamide Dose Modification**

If a patient experiences a  $\geq$  Grade 3 non-hematologic toxicity (except hypertension) attributable to enzalutamide or an intolerable side effect attributable to enzalutamide, withhold dosing for up to 1 month or until symptoms improve to  $\leq$  Grade 2, then resume at the same dose if clinically appropriate. If toxicity recurs and or in the judgment of the investigator dose reduction is appropriate, lower dose levels (120 mg /DL-1 or 80 mg/DL-2), may be considered. Enzalutamide may be discontinued if toxicity recurs and dose modification is no longer clinically appropriate.

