- 1.3.2.12 History of seizure, including any febrile seizure, loss of consciousness, or transient ischemic attack, or any condition that may pre-dispose to seizure (e.g., prior stroke, brain arteriovenous malformation, head trauma with loss of consciousness requiring hospitalization).
- 1.3.2.13 Other medications used for urinary symptoms including 5-alpha reductase inhibitors (finasteride and dutasteride) and alternative medications known to alter PSA (e.g., phytoestrogens and saw palmetto) cannot be taken while patients are receiving enzalutamide
- 1.3.2.14 Patients with a malignancy within the past 3 years for which study drugs or a prostatectomy is a contraindication.

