##### **1.10.1.1 Enzalutamide Dose Delay**

Enzalutamide may be started within 7 days if a dose is missed due to scheduling or logistical issues (e.g., vacation, weather) during the treatment period. If more than 7 days have elapsed, patients will need to be seen before further doses can be dispensed.

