### 1.10.2 Enzalutamide Dose Modification for Hypertension

If a patient experiences hypertension attributable to enzalutamide, patients should be optimally managed prior to withholding enzalutamide dose. Clinical judgment should be used in deciding whether the new or worsened hypertension emerging during treatment with enzalutamide requires immediate therapy.

Grade 2 ≥ 140 mmHg (systolic) and < 160 mmHg OR ≥ 90 mmHg (diastolic) and < 100 mmHg	
 
▪ Maintain dose of enzalutamide
 
▪ Increase antihypertensive therapy if clinically appropriate (consider increase dose of existing medications and/or add new antihypertensive medications)
 

Grade 3 ≥ 160 mmHg (systolic) OR ≥ 100 mmHg (diastolic)	
 
▪ Maintain dose of enzalutamide
 
▪ Increase antihypertensive therapy (increase dose of existing medications and/or add new antihypertensive medications)
 
▪ If optimal antihypertensive therapy does not result in a clinically significant reduction in blood pressure, enzalutamide should be held until blood pressure returns to baseline or < 140 / 90.
 

Grade 4	
 
▪ Discontinue enzalutamide
 

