### **1.16.4 Seizure threshold lowering drugs**

- Concomitant medications that can lower seizure threshold should be excluded during the course of this study, e.g., atypical antipsychotic drugs, phenothiazines, bupropion, aminophylline/theophylline, tricyclic and tetracyclic antidepressants, lithium, pimozide, venlafaxine.

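### Section 1.10.1 requires no enzalutamide stop after an on-treatment seizure, although the plan bars any seizure history and excludes threshold-lowering drugs during the study

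*Combined protocol and SAP*

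**What the plan says.** Seizure appears in two places. Exclusion criterion 1.3.2.12 bars men with "History of seizure, including any febrile seizure, loss of consciousness, or transient ischemic attack, or any condition that may pre-dispose to seizure". Section 1.16.4 carries the precaution into treatment: "Concomitant medications that can lower seizure threshold should be excluded during the course of this study". Neither says how to handle a seizure that occurs on the drug.

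The dosing text is as follows.

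- 1.9.1: "All patients will receive enzalutamide 160mg orally, daily for 24 weeks".
- 1.10.1, hold: for non-hematologic toxicity of Grade 3 or higher (hypertension apart) "attributable to enzalutamide or an intolerable side effect attributable to enzalutamide, withhold dosing for up to 1 month or until symptoms improve to" Grade 2 or lower, "then resume at the same dose if clinically appropriate". If toxicity recurs, or if the investigator judges a reduction appropriate, 120 mg or 80 mg may be considered.
- 1.10.1, stop: "Enzalutamide may be discontinued if toxicity recurs and dose modification is no longer clinically appropriate".
- 1.10.1.1, missed doses for logistical reasons: "If more than 7 days have elapsed, patients will need to be seen before further doses can be dispensed".
- 1.10.2, Grade 4 hypertension: "Discontinue enzalutamide".

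Section 1.16.1 lists unacceptable toxicity and the investigator's discretion among the grounds for removal from protocol therapy. For the former it cites only Section 3.3.1, which in the table-of-contents numbering is the section headed 1.10.1 in the text.

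**The concern.** The plan treats a past seizure as disqualifying whatever its cause or grade; a febrile seizure is enough. It also restricts other drugs during treatment for the same reason. A man who has a seizure while taking 160 mg daily would no longer meet 1.3.2.12, yet the rule that governs his next dose neither mentions the event nor requires him to stop.

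The stake is participant safety. Whether he continues a drug for which the plan itself takes seizure precautions is decided case by case, and two investigators could follow the protocol and decide differently. The removal criterion for unacceptable toxicity does not settle the matter, because it refers back to 1.10.1, which does not say which events qualify.

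**Working it through.** The plan gives no figure on this point. Its one design figure, an 83.6% chance of at least 10 men with significant residual disease among 50 at a rate of 25%, reproduces by the exact binomial tail (0.8363). It does not depend on the dose rule. The check is therefore mainly a reading of the text.

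**Step 1. Apply 1.10.1 to a seizure.**

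| Event | What 1.10.1 requires | What follows |
|---|---|---|
| Not attributed to enzalutamide | No hold | Dosing continues unless the investigator decides otherwise |
| Attributed, below Grade 3, not called intolerable | No hold | As above |
| Attributed, and Grade 3 or higher or intolerable | Hold | Same-dose restart if judged appropriate; a lower dose may be considered |
| Attributed and recurrent | No stop required | Discontinuation optional |

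**Step 2. Count the required enzalutamide stops in 1.10.** Grade 4 hypertension: 1. Seizure of any grade: 0.

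**Step 3. Full-dose exposure left open after one event.** Inputs: a 24-week course, or 24 × 7 = 168 days (1.9.1), and a maximum hold of 1 month (1.10.1). Assumptions: 1 month = 30 days = 30/7 = 4.29 weeks, and held doses are not made up. The event weeks are illustrative. For an event at week w, the remainder is 24 − w weeks with no hold and 24 − w − 4.29 weeks after a full hold.

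| Event at week | No hold: weeks left (share of course) | After a 30-day hold: weeks left |
|---|---|---|
| 4 | 20 (83%) | 15.7 |
| 8 | 16 (67%) | 11.7 |
| 12 | 12 (50%) | 7.7 |
| 16 | 8 (33%) | 3.7 |

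A hold shorter than a month falls between the two columns. These figures show how much dosing the rule leaves open. They do not measure harm, and the same subtraction would apply to any toxicity. The documents give no seizure rate, so no number of events is estimated.

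**Step 4. The wording of the hold.** The two ends of the hold, 1 month and recovery to Grade 2 or lower, are joined by *or*. The sentence does not say what happens if a month passes without recovery. Section 1.10.2 is clearer on a comparable case: for Grade 3 hypertension that optimal therapy does not control, enzalutamide is held until blood pressure recovers, with no time limit that ends the hold.

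**The case against.** The strongest reply is that an entry exclusion selects who starts and is not a stopping rule. The plan also excludes recent myocardial infarction, advanced heart failure and uncontrolled arrhythmia without a named on-treatment stop for each. Criterion 1.3.2.12 itself also covers loss of consciousness and transient ischemic attack, for which no stop is proposed here. This stands as a limit: it would be wrong to infer that every event named in the exclusions needs its own stop. Seizure differs because the plan carries the precaution into treatment, through 1.16.4. The plan also shows that it writes on-treatment rules when it wants them. Uncontrolled hypertension is an entry exclusion (1.3.2.5) and has a graded rule with a required stop (1.10.2).

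A reader might infer that the plan forces a rechallenge. It does not. Restart is conditional on clinical judgment, lower doses are available, and 1.16.1 allows removal at the investigator's discretion. The study calendar (1.14) provides an examination on day one of each treatment month, within 7 days either way. Under 1.25.1 the team meets weekly and the principal investigator reviews each patient's adverse events. These provisions allow a stop but do not require one.

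A reader might also infer that the hold wording licenses restart at 1 month with toxicity still above Grade 2. The words do not bar it, but the natural reading is a hold until recovery, for at most a month, with any restart still subject to judgment. That is one ambiguous conjunction and supports only a wording correction.

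Finally, 1.36 refers to the package insert for full agent information. The insert is not among the documents, so it cannot be said that investigators have no instruction anywhere. What can be said is that 1.10.1 gives none on seizure and does not point to the insert.

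**Conclusion.** The point holds as a gap in a participant-safety rule. Section 1.10 contains one required enzalutamide stop and none for seizure. Followed as written, the rule can leave a man on full-dose enzalutamide after an event that the plan treats as disqualifying at entry. It is worth correcting because the change is small and errs on the side of safety.

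The conclusion rests on the text of 1.3.2.12, 1.16.4, 1.10 and 1.16.1. It does not rest on an expected number of seizures. It would be a mistake to read it as a threat to the trial's results: it does not affect the primary objective, the sample size or the analysis. The ambiguity in the hold wording is secondary.

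**What to change.** Add to 1.10.1: *Permanently discontinue enzalutamide after any on-treatment seizure; goserelin, the second mpMRI and surgery continue as planned.*

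Leave 1.16.1 unchanged. It governs removal from protocol therapy, which in this single arm is enzalutamide and goserelin together. Listing a one-drug stop there would blur the two decisions.

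As a minor correction in the same section, let dosing resume only once toxicity is Grade 2 or lower, and discontinue enzalutamide if that is not reached within 1 month.

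The cost is an amendment of a few lines, with no added procedures or patients. The downside is lost latitude: a man whose seizure later proves unrelated forgoes his remaining enzalutamide (the shares of the course are in the table above), though he keeps goserelin, imaging and surgery. The plan does not quantify the benefit he would lose. If such a man were counted inevaluable, the accrual ceiling leaves room for 55 − 50 = 5.

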##### **1.10.1.1 Enzalutamide Dose Delay**

Enzalutamide may be started within 7 days if a dose is missed due to scheduling or logistical issues (e.g., vacation, weather) during the treatment period. If more than 7 days have elapsed, patients will need to be seen before further doses can be dispensed.

### 1.10.2 Enzalutamide Dose Modification for Hypertension

If a patient experiences hypertension attributable to enzalutamide, patients should be optimally managed prior to withholding enzalutamide dose. Clinical judgment should be used in deciding whether the new or worsened hypertension emerging during treatment with enzalutamide requires immediate therapy.

Grade 2 ≥ 140 mmHg (systolic) and < 160 mmHg OR ≥ 90 mmHg (diastolic) and < 100 mmHg	
 
▪ Maintain dose of enzalutamide
 
▪ Increase antihypertensive therapy if clinically appropriate (consider increase dose of existing medications and/or add new antihypertensive medications)
 

Grade 3 ≥ 160 mmHg (systolic) OR ≥ 100 mmHg (diastolic)	
 
▪ Maintain dose of enzalutamide
 
▪ Increase antihypertensive therapy (increase dose of existing medications and/or add new antihypertensive medications)
 
▪ If optimal antihypertensive therapy does not result in a clinically significant reduction in blood pressure, enzalutamide should be held until blood pressure returns to baseline or < 140 / 90.
 

Grade 4	
 
▪ Discontinue enzalutamide
 

## 1.11 IMAGING

### 1.11.1 mpMRI pre and post preoperative goserelin and enzalutamide

[figure not shown]
Patients will undergo pre-therapy ecoil MRI at 3T at screening. All MR data sets will be reviewed for quality and completeness. DCE PK analysis will be performed using commercially available iCAD software (<http://www.icadmed.com>). Post 6 months of preoperative therapy, a second ecoil MRI at 3T will be obtained. At both time points, quantitative T2, ADC values and DCE metrics will be extracted and recorded from all foci. DCE metrics to be collected include empirical indices such as Area Under the Curve at 90 seconds (AUC90) and Time to Peak (TTP), and also the derived indices  $K^{\text{trans}}$  (the forward volume transfer constant of Gadolinium between blood plasma and the interstitial space, expressed in units of  $\text{min}^{-1}$ ), and  $v_e$ , the dimensionless fractional volume of interstitial or extracellular space per unit volume of tissue. In addition, PiRads data will be collected for both time points.

### 1.11.2 Registration of pre- and post-therapy prostate MRIs

Drs. [name], [name], and [name] will collaborate on evaluation and registration of pre- and post-treatment MRIs. We will use non-rigid image registration for establishing correspondence between the targets and sub-areas in the baseline and post-therapy MR images. Preoperative therapies are known to significantly alter MR signal signatures for both normal and tumor tissue. [25, 26] We expect large reduction of the prostate gland from the baseline to post-treatment imaging session. These issues undoubtedly make the registration problem very challenging. Based on the limited preliminary evidence, intensity-based deformable registration based on Mutual information similarity metric pioneered by our group [27] can be used for co-registration of pre- and post-treatment prostate MRI. Our early preliminary results show the feasibility of such registration for the data collected in preoperative therapy cases (see [Figure 5](#) below). A

variety of deformable registration methods based on Mutual Information are available in 3D Slicer, [28] and will be applied to this problem. The transformations derived by the registration will be used to map the areas in the pre-treatment scans to the post-treatment gland configuration. This information will be used in manufacturing the custom mold that will include needle access to the image-registered locations of lesions to collect tissue samples from the ex vivo specimen.

**Figure 5:**

## 1.12 ON-TREATMENT EVALUATION

- Physical examination and vital signs
- Laboratory studies: **CBC with differential, PT/PTT, Acute care panel** (Serum sodium, Potassium test, Serum chloride, CO2, Creatinine, Glucose test, BUN); **Mineral panel** (Albumin, Calcium, Magnesium, Phosphorus – serum); **Hepatic Panel** (Alkaline phosphatase, ALT, AST, direct and total bilirubin); **LDH**; **Serum PSA**; and **Testosterone**
- Correlative studies (see Section 5.1)

## 1.13 FOLLOW UP PROCEDURES

After patient has completed their post-surgery visit, the patient will be contacted remotely (e.g., phone) annually up to five years by the research team to determine their PSA level. PSA levels may be obtained at NIH or through a local provider. If PSA recurs at 0.2 ng/mL or higher, the patient will come off study and will no longer be followed.

**Abbreviated Title:** Neoadjuvant ADT & Enzalutamide  
**Version Date:** 01/25/2024

### 1.14 STUDY CALENDAR

Procedure	Screen	Base-line	Day 1a						Post-Tx ----- Pre-Surgery	Post-Surgeryc	Follow upf
			Month 1	Month 2	Month 3	Month 4	Month 5	Month 6			
Physical Exam & Vital signs	X	X	X	X	X	X	X	X	X	X	
Performance Score	X	X									
Labs (See Sections 2.2 and 2.5)	X	X	X	X	X	X	X	X	X	X	
PSA	X	X	X	X	X	X	X	X	X	X	X
Pathologic Confirmation	X										
Biopsy	X e										
3T mpMRI	X e								X		
Correlative Research Studies b		X				X			X	X	
Imaging studies d	X								X		
ECG	X	X							X		
Prostatectomy									X		
Enzalutamide			X	→				X			
ADT			X			X					
Adverse Events		X	—					→ X			
Concomitant Medications		X	—					→ X			
Telephone call											X

a Assessments will be performed on day one of each month of treatment  $\pm$  7 days

b See Section 5.1 for information on correlative research

c Approximately 12 weeks after surgery, may be in combination with urology branch post-surgical visit

d Imaging studies, if clinically indicated, for disease evaluation within 12 weeks of study entry and pre-prostatectomy

e Performed within 6 months prior to starting protocol therapy

f Follow-up will be at least annually and may be done remotely (see Section 3.6).

## **1.15 COST AND COMPENSATION**

### **1.15.1 Costs**

NIH does not bill health insurance companies or participants for any research or related clinical care that participants receive at the NIH Clinical Center. If some tests and procedures are performed outside the NIH Clinical Center, participants may have to pay for these costs if they are not covered by insurance company. Medicines that are not part of the study treatment will not be provided or paid for by the NIH Clinical Center.

### **1.15.2 Compensation**

Participants will not be compensated on this study.

### **1.15.3 Reimbursement**

The NCI will cover the costs of some expenses associated with protocol participation. Some of these costs may be paid directly by the NIH and some may be reimbursed to the participant/guardian as appropriate. The amount and form of these payments are determined by the NCI Travel and Lodging Reimbursement Policy.

## **1.16 CRITERIA FOR REMOVAL FROM PROTOCOL THERAPY AND OFF STUDY CRITERIA**

Prior to removal from study, effort must be made to have all subjects complete a safety visit approximately 30 days following the last dose of study therapy.

### **1.16.1 Criteria for removal from protocol therapy**

- Completion of protocol therapy
- Participant requests to be withdrawn from active therapy
- Unacceptable Toxicity (Section [3.3.1](#)).
- Investigator discretion

### **1.16.2 Off-Study Criteria**

- Completed study follow-up period (Follow-up period will be 5 years or until PSA recurrence of 0.2 ng/mL whichever is sooner)
- Initiation of new therapy
- Participant requests to be withdrawn from study
- Death
- Study is cancelled

## **CONCOMITANT MEDICATIONS/MEASURES**

Patients may be on concomitant drugs to prevent bone loss, including calcium, vitamin D, bisphosphonates and denosumab.

Other supportive care with blood components, antibiotics, analgesics, general medical therapy, etc., will be delivered as required.

### **1.16.3 General Guidelines**

All medications (other than study drug) and significant non-drug therapies (including physical therapy and blood transfusions) taken within 28 days of starting study treatment through the 6 to 10 week safety follow up visit should be reported on the CRF.

While patients on protocol treatment, all medications required for the health of the patient are allowed with the following exceptions:

- Concurrent chemotherapy
- Concurrent radiation therapy
- Concurrent immunotherapy
- Concurrent anti-cancer radionuclides
- Concurrent systemic corticosteroid use (daily or every other day for continued use **>14 days**)
- Concomitant use of secondary hormonal treatments
- Concomitant use of herbal supplements

### **1.16.4 Seizure threshold lowering drugs**

- Concomitant medications that can lower seizure threshold should be excluded during the course of this study, e.g., atypical antipsychotic drugs, phenothiazines, bupropion, aminophylline/theophylline, tricyclic and tetracyclic antidepressants, lithium, pimozide, venlafaxine.

### **1.16.5 Cytochrome P450 and P-glycoprotein**

- Co-administration of enzalutamide with strong or moderate CYP2C8 inducers (e.g., rifampin) may alter the plasma exposure of enzalutamide. Moderate CYP2C8 inducers may be used concomitantly with enzalutamide at the investigator's discretion. If co-administration of enzalutamide with a strong CYP2C8 inhibitor cannot be avoided, reduce the dose of enzalutamide to 80 mg per day.
- Co-administration of enzalutamide with strong CYP3A4 inducers (e.g., carbamazepine, phenobarbital, phenytoin, rifabutin, rifampin, rifapentine) may decrease the plasma exposure of enzalutamide and should be avoided if possible. Selection of a concomitant medication with no or minimal CYP3A4 induction potential is recommended.
- Moderate CYP3A4 inducers (e.g., bosentan, efavirenz, etravirine, modafinil, nafcillin) and St. John's Wort may also reduce the plasma exposure of enzalutamide and should be avoided if possible.
- Concomitant use of enzalutamide with narrow therapeutic index drugs that are metabolized by CYP3A4 (e.g., alfentanil, cyclosporine, dihydroergotamine, ergotamine, fentanyl, pimozide, quinidine, sirolimus and tacrolimus), CYP2C9 (e.g., phenytoin, warfarin) should be avoided, as enzalutamide may decrease their exposure.
- Grapefruit, Seville oranges, and starfruit affect P450 and PgP activity. Concomitant use should be avoided.

**CORRELATIVE STUDIES FOR RESEARCH****1.17 BIOSPECIMEN COLLECTION**

Note: Tubes and media may be substituted based on availability with the permission of the PI or laboratory investigator.

**1.17.1 Histopathological Analysis**

After localization by MR of the desired pretreatment and post treatment biopsy sites, one or two immediately adjacent tissue cores will be obtained from the lesion. One core will be placed in formalin (FFPE) for processing for histopathology, to confirm tumor diagnosis, Gleason grade and extent of tumor. The second core, if obtainable (presumed to be nearly identical in features to the first core), will be reserved for molecular analyses detection of androgen receptor variants. This analysis will be done only if there is sufficient tissue and after obtaining informed consent.

Clinical protocol steps	Procedures	Core pathology analyses
Pre-treatment (MR 1): MRI Index lesion(s) identified	In vivo Biopsy  Index lesion(s)  Optional biopsy	#1: FFPE (histology)  #1A FFPE & 1 H&E (molecular analyses)  #2: Fresh frozen (optional)
ADP Therapy	Prostatectomy	Full pathology report issued
Post-treatment (MR 2): MRI Index lesion(s) identified (same lesion(s) as above)	Ex Vivo Biopsy  Index lesion(s)  Optional biopsy	#1: FFPE (histology)  #1A FFPE & 1 H&E (molecular analyses)  #2: Fresh frozen (optional)

